4.3 Exclusion criteria

A potential subject who meets the following criteria will be excluded from participation in this study:

- Patients that on the original informed consent form of the STITCH trial, checked the box that they did not want to be approached for future follow-up studies.
- Patients who withdrew their informed consent during the original STITCH trial.

4.4 Sample size calculation

The original STITCH trial ended up with 545 patients completing the 1-year follow-up.

5. TREATMENT OF SUBJECTS

5.1 Investigational product/treatment

Not applicable as this is a follow-up study of a previous RCT. The surgical treatments have already taken place.

5.2 Use of co-intervention

Not applicable as no co-intervention is used in this study.

5.3 Escape medication

Not applicable. This study will not use any escape medication.

6. INVESTIGATIONAL PRODUCT

6.1 Name and description of investigational product

Not applicable as no investigational product is used in this study.

6.2 Summary of findings from non-clinical studies

Not applicable as no investigational product is used in this study.

6.3 Summary of findings from clinical studies

Not applicable as no investigational product is used in this study.

6.4 Summary of known and potential risks and benefits

Not applicable as no investigational product is used in this study.

6.5 Description and justification of route of administration and dosage

Not applicable as no investigational product is used in this study.

6.6 Dosages, dosage modifications and method of administration

Not applicable as no investigational product is used in this study.

6.7 Preparation and labelling of Investigational Medicinal Product

Not applicable as no investigational product is used in this study.

6.8 Drug accountability

Not applicable as no investigational product is used in this study.

7. NON-INVESTIGATIONAL PRODUCT

7.1 Name and description of non-investigational product(s)

Not applicable as no non-investigational product is used in this study.

7.2 Summary of findings from non-clinical studies

Not applicable as no non-investigational product is used in this study.

7.3 Summary of findings from clinical studies

Not applicable as no non-investigational product is used in this study.

7.4 Summary of known and potential and benefits

Not applicable as no non-investigational product is used in this study.

7.5 Description and justification of route of administration and dosage

Not applicable as no non-investigational product is used in this study.

7.6 Dosages, dosage modifications and method of administration

Not applicable as no non-investigational product is used in this study.

7.7 Preparation and labelling of Non Investigational Medicinal Product

Not applicable as no non-investigational product is used in this study.

7.8 Drug accountability

Not applicable as no non-investigational product is used in this study.

8. METHODS

8.1 Study parameters/endpoints

8.1.1 Main study parameter/endpoint

The primary outcome measure is the 10-year midline incisional hernia rate. The size (diameter) and location of the hernia will be documented.

In patients who died during follow-up, this will be evaluated by reviewing the available medical charts and radiological studies. CT-scans of the abdomen will be evaluated by the study-team. If CT imaging is not available, documented findings during physical examination by the relevant medical specialist will be considered. The CT scans of patients being still alive will be reassessed for an incisional hernia.

8.1.2 Secondary study parameters/endpoints

The secondary outcomes will be measured using five validating questionnaires. Quality of Life (QoL), body image, cosmetic results and abdominal wall function (AWF) will be reported from all patients who are still alive with consent for participation. Three of the five questionnaires have also been validated in a Dutch version. The other two were translated from English. The following measuring instruments will be used for this:

- Quality of Life
 - MOS SF-36: This questionnaire consists of 36 items. The item scores are summed to scale scores and transformed to a 100-point scale. A higher score indicates better health status(9).
 - EQ-5D; This questionnaire consists of a total of fourteen items. The answers can be converted to a total score representing the health profile(10).
- Body image: Dresden Body Image Questionnaire (DBIQ); consists of 35 items and five subscales (11).
- Cosmetic results: Body Image Questionnaire (BIQ); the questionnaire consists of ten items evaluating body image, cosmesis and self-confidence before and after surgery. The higher the score in the first five items, the lower the body image. The lower the score in items 6, 7 and 8, the lower cosmesis assessment. The last two items are about self-confidence before and after surgery where 1 is "not very confident" and 10 is "very confident." (12).
- AWF: Hernia-Related Quality of Life Survey (HerQLes); this questionnaire consists of twelve statements where the patient can choose from six options, how much they agree or disagree with the statement. The higher the score, the greater the burden of the abdominal wall(13).

8.1.3 Other study parameters

Demographic characteristics collected during randomization during the original trial are used for follow-up. This includes gender, age, length and weight (BMI), smoking history (yes or no), medical history and ASA class.

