2. OBJECTIVES

Primary Objective:

The primary objective of the original STITCH trial was reduction of the incidence of an incisional hernia after open, elective abdominal surgery. The primary objective of the present study is to determine the difference in incidence of incisional hernia between the intervention group and the control group of the original STITCH trial after 10 years of follow-up from the time of randomization,.

Secondary Objectives:

The secondary objectives of this follow-up study are to measure quality of life (QoL), body image and cosmetic results and abdominal wall function in those patients who are still alive.

[figure not shown]
In addition, all information is collected regarding the abdominal wall hernia (presence, location, duration, size, recurrence, repair) and other abdominal wall related complications such as: open abdomen, enterocutaneous fistula, wound problems, burst abdomen, number of abdominal reoperations, number of hospital admissions (and total days) with/without development of ileus.

STUDY DESIGN

The original STITCH trial (NCT01132209) was a multicenter double-blind prospective randomized controlled trial who randomly assigned 560 patients between October 2009 and March 2012 in the intervention group (small bites) or in the control group (large bites). Ultimately, 268 patients were included in the intervention group and 277 patients in the control group. A total of 545 patients.

This current study is a long-term (10-13 years) follow-up of the original STITCH trial.

The flowchart below graphically depicts the process of approaching the patients who were included in the original STITCH trial. On the original informed consent form of the STITCH trial patients were asked if they agreed to being contacted for a follow-up study after completion the original trial.

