10. STATISTICAL ANALYSIS

10.1 Primary study parameter(s)

We will analyse the primary outcome for the 545 patients using Kaplan Meier analysis and log-rank test to compare the two trial groups based on an intention-to-treat basis (7). Statistical analyses will be performed using IBM® SPSS® Statistics Version 29. In the case of missing data, a regression model is used to estimate the missing values.

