10.3 Other study parameters

Demographics and baseline characteristics will be reported using descriptive statistics.

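### The primary comparison uses no baseline covariates although they were collected at randomisation; a pre-specified adjusted analysis beside the log-rank test may add power and weakens the censoring assumption

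*Protocol*

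**What the plan says.** Protocol section 10.1 fixes the primary analysis: "We will analyse the primary outcome for the 545 patients using Kaplan Meier analysis and log-rank test to compare the two trial groups". The stated principle is intention to treat. The section names no covariate and no stratum.

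Section 8.1.3 describes the baseline data: "Demographic characteristics collected during randomization during the original trial are used for follow-up". The variables themselves are then listed in that section: "This includes gender, age, length and weight (BMI), smoking history (yes or no), medical history and ASA class".

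The only analytic role that section 10 states for these variables is in 10.3: "Demographics and baseline characteristics will be reported using descriptive statistics".

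Section 10.1 also mentions a regression for missing data: "In the case of missing data, a regression model is used to estimate the missing values". Its predictors are not named. It concerns filling in values, so it cannot be read as covariate adjustment of the comparison between arms.

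**The concern.** The cohort is closed. Section 4.4 gives 545 patients and no power, alpha, effect size or event target, and section 8.5 says nobody can be replaced. Precision therefore has to come from the analysis, and adjustment for prognostic baseline variables is one of the few routes left.

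The second issue is censoring. Follow-up runs 10 to 13 years. Patients who died are assessed from whatever charts and scans exist (8.1.1), and living patients contribute only with new consent (4.2). Age and ASA class plausibly affect survival and attendance, and BMI and smoking plausibly affect hernia risk. A Kaplan-Meier 10-year rate is unbiased only if leaving follow-up is unrelated to hernia risk within the arm. An adjusted model needs this only among patients with the same recorded covariates.

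**Working it through.** **Document inputs.** The Study Design section states: "Ultimately, 268 patients were included in the intervention group and 277 patients in the control group". 268 + 277 = 545, which agrees with 4.4 and 10.1. Section 1 gives 1-year hernia rates of 13% (small bites) and 21% (large bites).

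**No power figure to reproduce.** Section 4.4 states none. For context only, assuming two-sided alpha 0.05 (not in the protocol), at the 1-year rates:

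- Hernias: 268 × 0.13 + 277 × 0.21 = 34.84 + 58.17 ≈ 93.
- Two proportions: pooled rate 93.01/545 = 0.1707; SE under the null 0.0322, under the alternative 0.0320. Power = Φ[(0.08 − 1.96 × 0.0322)/0.0320] ≈ 70%.
- Schoenfeld: HR = ln(0.87)/ln(0.79) = 0.591; allocation 268/545 = 0.492. Power = Φ[√(93 × 0.492 × 0.508) × |ln 0.591| − 1.96] ≈ 72%.

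At these rates there is room for a gain in precision.

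**Effect of adjustment on power (every scenario input assumed).** Arms of 268 and 277; exponential hernia times; control hazard 0.04 a year at the average covariate value; conditional HR 0.65; censoring 0.07 a year, rising with the covariate equally in both arms; follow-up capped at 10 years; 2,000 runs per row. The covariates are represented by one standardised baseline score, and its SD on the log-hazard scale is the prognostic strength.

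| SD of score | Events | Log-rank | Adjusted Cox | Gain (points) |
|---|---|---|---|---|
| 0 | 110 | 60.5% | 60.0% | −0.5 |
| 0.3 | 109 | 57.7% | 58.0% | +0.3 |
| 0.5 | 111 | 57.0% | 59.2% | +2.2 |
| 0.8 | 119 | 58.7% | 65.0% | +6.3 |
| 1.0 | 125 | 55.9% | 66.8% | +10.9 |

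The Monte Carlo standard error of each power figure is about √(0.6 × 0.4/2000) = 1.1 points, so the first two rows show no real difference.

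A second simulation used five covariates, 10-year control risk 35%, HR 0.65, death 5% a year and about 130 to 155 hernias, and compared Cox models without and with the covariates. Power went from 66% to 68%, 64% to 68% and 59% to 67% at SD 0.4, 0.6 and 0.8. Type I error was 3.5% to 5.6%. Direction and rough size agree.

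**Effect of censoring on the between-arm test (no true effect).** Same set-up with HR 1 and base censoring 0.10 a year; SD 0.3, 0.5 and 0.8 in turn.

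| Censoring pattern | Log-rank size | Adjusted size |
|---|---|---|
| Depends on covariate equally in both arms | 5.0, 4.2, 5.0% | 4.7, 3.6, 5.1% |
| Same dependence, rate higher in one arm (0.15 against 0.10) | 5.2, 5.4, 5.1% | 4.9, 5.0, 3.9% |
| Depends on covariate in one arm only | 7.1, 11.4, 17.0% | 4.2, 5.4, 6.0% |

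In the second pattern the unadjusted HR drifts slightly, from 0.97 to 0.94. In the third it moves to 1.08, 1.14 and 1.19 although the true value is 1. Only the third pattern damages the test materially.

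**Effect of censoring on the 10-year rates.** A large-sample simulation assumed a true control risk of 35%, HR 0.65, censoring about 8% a year, and one score driving both hernia (SD 0.4 to 0.8) and censoring (SD 0.5 to 0.8, either direction at 0.5). Kaplan-Meier gave control risks between 29.4% and 38.3%, an error of about 2 to 6 points. The risk difference moved by less than 1 point, because both arms shift together.

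**The case against.** The strongest reply is that nothing here is wrong. An unadjusted intention-to-treat log-rank test between randomised arms is a valid primary analysis, and adjusted or sensitivity models are often left to an SAP, which is not at hand. This stands as far as validity goes. It does not remove the point, because the protocol itself names both the primary method and the role of the baseline data.

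A reader might infer that power is certainly being lost. The documents do not support that: they give no prognostic strength for any covariate, and the gain is nil if the covariates are not prognostic.

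A reader might also infer that covariate-related death and non-attendance invalidate the log-rank test. They do not when the dependence is the same in both arms. Nothing in the protocol shows that it differs by arm, and nothing excludes it. The protocol gives no figure for how many patients leave through death or lack of consent.

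Nor do the documents show that the baseline values are complete. Section 8.1.3 says when they were collected, not that none are missing.

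Finally, making an adjusted Cox model primary would have a price. It targets a conditional hazard ratio, relies on proportional hazards over 10 years, and would change the primary method after the 1-year results by arm are known. That argues against replacing the log-rank test. It does not argue against a pre-specified adjusted analysis beside it.

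**Conclusion.** The point holds as a modest, inexpensive improvement. The protocol compares the arms without baseline adjustment and gives covariates collected at randomisation only a descriptive analytic role. The possible power loss is about 0 to 2 points with weak to moderate covariates and about 6 to 11 with strong ones. These figures rest on assumed HR, hazards, censoring and prognostic strength.

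The 10-year rates within each arm could be off by a few points if the covariates drive both hernia and censoring. Under the assumptions tested, the difference between arms is much less affected. The log-rank test itself is at material risk only under arm-specific dependence, which remains a possibility and is not shown.

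The documents do not support calling the planned analysis invalid or demoting the log-rank test.

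**What to change.** In section 10.1, keep the Kaplan-Meier curves and the log-rank test. Add a pre-specified Cox model for time to incisional hernia with arm plus baseline age and BMI (both continuous), gender, smoking and ASA class, reported beside the log-rank test as the covariate-adjusted treatment effect. Optionally, report 10-year risks by arm standardised over the same covariates, since the endpoint is a rate. Fix the covariate list, the coding of ASA class and the handling of missing baseline values before the long-term outcomes are analysed, so that the adjustment cannot look data-driven.

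The cost is a few lines of text and some extra analysis, mainly for the standardised risks; no new data collection is planned for it. The covariates use about five to seven degrees of freedom (four for age, BMI, gender and smoking, one to three for ASA class), against about 93 hernias already implied at one year. The adjusted hazard ratio is conditional on the covariates and relies on proportional hazards, which should be checked.

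The change does not deal with death as a competing event or with non-consent driven by factors that were not recorded.

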8.2 Randomisation, blinding and treatment allocation

Not applicable as no additional randomisation or blinding will be performed in this study. Patients had already been randomized at the time they were included in the original RCT.

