Main study parameters/endpoints: The primary outcome measure is the 10-year midline incisional hernia rate. The primary endpoint will be determined for the 545 patients of the original intention-to-treat population using Kaplan Meier analysis. In patients who died during follow-up, this will be evaluated by reviewing the available medical charts and radiological studies. CT-scans of the abdomen will be evaluated by the study-team. If CT imaging is not available, documented findings during physical examination by the relevant medical specialist will be considered. Patients being still alive with written informed consent to be contacted will be approached for their willingness to participate in this follow-up study, and after consent, we will reassess CT scans for an incisional hernia. All patients who are still alive and want to participate in this study will be asked to visit the hospital once for physical examination and an ultrasound of the abdominal wall. Secondary outcome parameters include QoL and cosmetic outcome, Patients still alive with consent for participation will be sent the following questionnaires: MOS SF-36 and EQ-5D (QoL), Dresden Body Image Questionnaire (body image), Body Image Questionnaire (cosmesis), Hernia-Related Quality of Life Survey (abdominal wall function). Furthermore, readmission and surgical intervention rates related to midline IH will be determined for the entire study population.

Nature and extent of the burden and risks associated with participation, benefit and group

relatedness: Undergoing an ultrasound, physical examination and completing several questionnaires may be considered burdensome for the patient.

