8.3 Study procedure

Of patients still alive who want to participate in the follow-up study and patients who have died, the medical record and any available radiological imaging are reviewed retrospectively by members of the study team.

All patients who are still alive and want to participate in this study will be asked to visit the hospital once for physical examination and an ultrasound of the abdominal wall. Subsequently, all those patients will be asked to complete five validated questionnaires related to quality of life, cosmesis, body image and abdominal wall function. There is no set time after randomization in the original STITCH trial when the questionnaires should be completed. Indeed, this would mean that data collection would have to spread out over a few years which is not desirable.

After the physical examination and ultrasound are performed, the patient is given a brief explanation of the five questionnaires to be completed. The patient can choose whether to complete these questionnaires digitally at home or on paper at home (and return them free of charge).

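### Section 8.2 adds no blinding, although the 10-year hernia outcome rests on new CT and record judgements and nothing keeps those assessors unaware of closure technique

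*Protocol*

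**What the plan says.** Section 8.2 is the protocol's only section on blinding. It reads "Not applicable as no additional randomisation or blinding will be performed in this study" and gives as its reason that randomisation took place in the original trial.

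The primary outcome is the 10-year midline incisional hernia rate, and it is established by new work:

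- For patients who died, section 8.1.1 says "CT-scans of the abdomen will be evaluated by the study-team", with documented examination findings as the fallback where there is no CT.
- For living patients, the same section says "The CT scans of patients being still alive will be reassessed for an incisional hernia". The Summary says this too: "after consent, we will reassess CT scans for an incisional hernia".
- For both groups, section 8.3 says "the medical record and any available radiological imaging are reviewed retrospectively by members of the study team".
- Living participants are also asked to "visit the hospital once for physical examination and an ultrasound of the abdominal wall". The Summary puts this visit in its paragraph on the main endpoint. Section 8.1.1 does not mention it, and section 8.3 describes it without tying it to the endpoint.

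The study design section says that the original trial "was a multicenter double-blind prospective randomized controlled trial". Section 10.1 compares the two arms by Kaplan-Meier analysis and a log-rank test.

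**The concern.** Randomisation in 2009 to 2012 made the arms comparable. It does not stop someone who reads a scan today from being influenced by the arm, if that person knows it. The reason given in section 8.2 therefore explains why no new randomisation is needed, but not why masking of assessors would be unnecessary.

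The hernia definition cited in the Introduction includes gaps that do not bulge and accepts either examination or imaging, so borderline findings are plausible. The Introduction also reports the 1-year result in favour of small bites (13% against 21%), so the team that judges the outcome knows which way the first result went. If equivocal scans or records were classified differently by arm, the error would pass straight into the primary comparison. A log-rank test takes the recorded events as given and cannot detect or correct it. Readings made with the allocation known cannot be made masked afterwards, so the protection has to be in place before the readings start.

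**Working it through.** **Does any section protect the assessors?** The places that could do so are these:

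| Place in the protocol | What it covers | Masks the new assessors? |
|---|---|---|
| Study design | Double-blind conduct of the original trial | No; nothing extends it to the follow-up |
| 8.1.1 and Summary | CT evaluation and reassessment | No condition on knowledge of the arm |
| 8.3 | Record and imaging review by team members | No condition |
| 8.2 | Blinding | None added |
| 12.1 | Patient code with a letter for the site | The code carries no arm information, but nothing says assessors work from coded data only |
| 12.2 | Check of a 10% sample for correctness and completeness | No masked second reading |

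No section states that a CT reader or record reviewer is unaware of closure technique.

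**How large could the effect be?** The protocol gives no figure to reproduce, so this is an illustration only.

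Input from the study design section: "268 patients were included in the intervention group and 277 patients in the control group", 268 + 277 = 545 in total.

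Assumptions, none of them from the protocol:

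- true 10-year incidence 30% in both arms;
- share of equivocal patients e = 10% (range 5% to 15%);
- gap between arms in how often an equivocal case is called a hernia g = 20 points (range 10 to 30);
- fraction of patients newly judged f = 1, or f = 0.5;
- two-sided 5% test, normal approximation for two proportions.

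Spurious difference: b = e × g × f.

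- f = 1: 0.10 × 0.20 = 0.020 (0.05 × 0.10 = 0.005 to 0.15 × 0.30 = 0.045).
- f = 0.5: 0.010 (0.0025 to 0.0225).

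Standard error: SE = √[0.3 × 0.7 × (1/277 + 1/268)] = 0.0393.

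Type I error = 1 − Φ(1.96 − b/SE) + Φ(−1.96 − b/SE).

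| | b, points | Type I error, SE 3.93 points | Type I error, SE 5 points (assumed, to allow for censoring) |
|---|---|---|---|
| f = 1 | 2.0 (0.5 to 4.5) | 8.0% (5.2% to 20.9%) | 6.9% (5.1% to 14.7%) |
| f = 0.5 | 1.0 (0.25 to 2.25) | 5.8% (5.1% to 8.8%) | 5.5% (5.0% to 7.4%) |

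The upper ends need both extreme assumptions at once.

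The protocol does not say whether 1-year hernia status is carried forward. No type I error is given for that case: about 58 hernias (0.21 × 277) against 35 (0.13 × 268) would already be fixed, and an error rate computed under a zero-difference null would not fit that imbalance.

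**The case against.** The strongest reply is that section 8.2 can be read as meaning that the original allocation and blind simply stand. It says that nothing is added; it does not say that assessors are unmasked or may see the allocation. That is fair. A reader might infer that the sponsor chose open assessment, and the wording does not support this. What remains is that no section carries the original blind over to people who judge the outcome years after the arm-level result was reported. If continued masking is intended, one sentence would settle it.

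Second, bias needs an assessor who knows the arm, findings that are equivocal, and judgements that differ by arm. The protocol documents none of these. Knowing that small bites did better at 1 year is not knowing any patient's allocation, and the protocol does not say that a scan, record or operation note reveals the technique. This objection stands in full as a limit on the claim.

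Third, the visit should not carry the same weight as CT and record review. That also stands: only the Summary places the examination and ultrasound with the main endpoint.

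Fourth, this might be left to a statistical analysis plan. That does not hold. Who reads scans, and with what access, is trial conduct, and the protocol has a section for it.

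**Conclusion.** The point holds as missing protection of the primary outcome. It is firm for CT evaluation and record review, and looser for the survivors' examination and ultrasound. Section 8.2 treats blinding as not applicable, when new judgements make it applicable.

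A reader might go further and conclude that assessors will know the arm, or that the 10-year result will be biased towards small bites. The protocol supports neither: it shows no unmasked assessor, no bias and no direction.

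The size is unknown. The illustrative figures run from negligible to moderate and rest wholly on assumed shares of equivocal cases and assumed gaps between arms, so they do not carry the conclusion. The case for acting rests on the general value of masked outcome assessment and on the low cost of securing it. This is a cheap improvement, not the correction of a demonstrated error.

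**What to change.** Replace the text of section 8.2 with wording to this effect:

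> No new randomisation takes place. CT readers judge the hernia outcome without access to the allocation or the index operation note. Record reviewers, examiners and sonographers do so as far as feasible. Hernia presence, date and size are entered and locked in the study database before allocation is merged. Any assessment made with the allocation known is flagged, and the number is reported by arm.

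The change concerns wording, database access rights and the order of work, and adds no procedure for patients. Its cost is that tasks and access rights must be divided within the existing team, whose size the protocol does not give. Keeping operation notes from record reviewers may be harder than masking CT readers, because reviewers also collect reoperations, burst abdomen and admissions and may need the full record. Masking therefore stays incomplete for those reviewers. It also stays incomplete for findings that treating specialists have already documented, which includes the fallback where no CT exists. The count of unmasked assessments by arm makes that remainder visible.
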